## 1.6 Research Risks & Benefits

### 1.6.1 Risk of Study Drug

Study drug risks with Vyvanse (Lisdexamfetamine Dimesylate) are decreased appetite, insomnia, upper abdominal pain, irritability, nausea and vomiting, weight decreased, dry mouth, dizziness, affect lability, rash, diarrhea, anxiety, anorexia, jittery feeling, and agitation. Patients will be told to take medication once daily in the morning and report if they have any of these effects at each visit [10].

Warnings and Precautions with Vyvanse (Lisdexamfetamine Dimesylate) are sudden death, stroke, and myocardial infarction (MI) reported in adults. Sudden death reported in children and adolescents with structural cardiac abnormalities and other serious heart problems [10]. Patients will have an electrocardiograph (EKG) prior to induction on Vyvanse (Lisdexamfetamine Dimesylate). Subjects will be monitored weekly for hypertension, tachycardia and any cardiac abnormalities. People with heart abnormalities will not be treated with amphetamines. These serious but uncommon side effects were reported by people who took Vyvanse. The following cardiovascular side effects (involving the heart and/or blood vessels) have been reported with the use of amphetamines:

- Sudden death
- Cardiomyopathy (enlargement of the heart or muscle weakness)
- Myocardial infarction (heart attack)
- Increased blood pressure
- Tachycardia (rapid heart rate)
- Palpitations (forceful, sometimes irregular heartbeats)

Vyvanse (Lisdexamfetamine Dimesylate) may exacerbate symptoms of behavior disturbance and thought disorder in patients with a preexisting psychotic disorder. Vyvanse may induce a mixed/manic episode in patients with bipolar disorder. Patients will be screened for any preexisting Axis 1 diagnosis, which would exclude them from the study.

CONFIDENTIAL

The following uncommon central nervous system side effects involving the brain and/or spinal cord have been reported with the use of amphetamine: stroke, psychotic episodes, mania, euphoria, depression, dysphoria, overstimulation, aggressive behavior, hostility, seizures, tremor, dyskinesia, exacerbation of phonic tics including Tourette's syndrome or motor tics, blurry vision, dizziness, restlessness, and headache. If during the course of the study patient develops any of these side effects including changes in mood, the study doctor will discontinue patient from the study and refer the patient to regular treatment.

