## **6 Study Procedures:**

CONFIDENTIAL

This material is the property of the NYU School of Medicine and Langone Medical Center. Do not disclose or use except as authorized in writing by the study sponsor

	Visit 1	Visit 2	Visit 3	Visit 4	Visit 5	Visit 6	Visit 7	Visit 8	Visit9	Visit 10	Visit 11
Study Procedures and Assessments	Week -3-0	Week 0	Week 1	Week 2	Week 3	Week 4	Week 6	Week 7	Week 8	Week 9	Week 10
	Screening	Baseline 1	Treatment (LDX or PBO) 1			EOT 1	End of PBO Washout/ Baseline2	Treatment (LDX or PBO) 2			EOT 2
SCREENING											
Consent	X										
Demographics	X										
M.I.N.I	X										
ACDS v1.2	X										
Medical History	X										
Psychiatric History	X										
Medical Review of Systems	X										
Physical Exam	X										
Hematology, Chemistry, Urinalysis, and UDS	X										
Urine Pregnancy Test	X										
ECG	X										
Review Eligibility	X	X	X								
EFFICACY											
ADHD-RS		X		X	X	X	X	X	X	X	X
Barkley SCT Scale		X		X	X	X	X	X	X	X	X
CGI-S		x		X	X	X	X	X	X	X	X
SAFETY											
Vital Signs		X	X	X	X	X	X	X	X	X	X
C-SSRS		X	X				X	X			X
Concomitant Medications		X	X	X	X	X	X	X	X	X	X
Adverse Events		X	X	X	X	X	X	X	X	X	X
NEUROPSYCHOLOGICAL BATTERY/EXECUTIVE FUNCTIONING											
CANTAB ADHD		x					X	X			X
WAIS-CODING & SYMBOL SEARCH		X					X	X			X
BRIEF-A		X					X	X			X
BFIS		X					X	X			X
ON-TOP		X									
OTHER											
Dose Dispense/ Adjustment			X	X	X	X			X	X	X
Drug Accountability				X	X	X	X	X	X	X	X

CONFIDENTIAL

This material is the property of the NYU School of Medicine and Langone Medical Center. Do not disclose or use except as authorized in writing by the study sponsor

**STUDY VISIT SCHEDULE:** This is a two part study. Patients will sign this consent form and be asked to do the following: Visit the study doctor weekly over a 12-week period, communicate over the phone between visits 6 and 7 and approximately 1 week after visit 10, and follow study instructions. In addition, patients who participate in the second part of the study will be asked to take study drug as instructed at the same time each day. Patient will have their blood drawn once in the study about 10mls will be collected for hematology and blood chemistry.

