**6.3 Visits 3, 4, & 5 (Treatment) Day 7±2, Day 14 ±2, and Day 21±2; Weeks 1-3**

Visits 3, 4, and 5 will occur at 7, 14, and 21 days (±2 days) from Baseline. These visits will consist of ADHD-RS with prompts, Barkley SCT Scale, CGI, vital signs, and assessment of adverse events (AE) and concomitant medications (CM). Study Medication is dispensed.

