**6.4 Visit 6 (EOT1) Day 28±2; Week 4**

Visit 6 will consist of ADHD-RS with prompts, Barkley SCT Scale, BRIEF-A, Barkley Functional Impairment Scale (BFIS), neuropsychological battery, CGI, vital signs, assessment of adverse events (AE) and concomitant medications (CM). Study Medication is dispensed. Drug accountability performed. Patient will receive *two* study medication bottles.

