## **6.8 Visit 11 End of Treatment 2; Day 70±2 Week 10**

End of treatment will consist of ADHD-RS with prompts, Barkley SCT Scale, BRIEF-A, Barkley Functional Impairment Scale (BFIS), C-SSRS, neuropsychological battery, CGI, vital signs, assessment of adverse events (AE) and concomitant medications (CM). Drug accountability is performed.

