Safety Analysis: Variables to be summarized and listed include vital signs, adverse events, clinical laboratory results, ECG readings, and the C-SSRS. All adverse events results will be tabulated in manuscripts along with significance testing using the appropriate general linear model. These models will use LOCF endpoint analyses with terms for drug, order and the drug by order interaction

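### ECG and laboratory tests are scheduled only at screening, and no C-SSRS is scheduled at the end of block 1, so these safety summaries cannot support an LDX–placebo statement (for the C-SSRS, not one at the end of both blocks)

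*Combined protocol and SAP*

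**What the plan says.** The Safety Analysis paragraph of section 7.2 has three sentences. The first names the variables: "Variables to be summarized and listed include vital signs, adverse events, clinical laboratory results, ECG readings, and the C-SSRS". The second concerns adverse events: "All adverse events results will be tabulated in manuscripts along with significance testing using the appropriate general linear model". The third describes those models: "These models will use LOCF endpoint analyses with terms for drug, order and the drug by order interaction".

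The schedule table in section 6 marks the ECG and the hematology, chemistry and urinalysis panel at Visit 1 and nowhere else. The paragraph below the table confirms this for blood: "Patient will have their blood drawn once in the study". Section 6.1 lists the ECG and laboratory tests at screening, and sections 6.2 to 6.8 do not schedule them again. Section 1.6.1 places the ECG before the start of LDX, yet also says: "Subjects will be monitored weekly for hypertension, tachycardia and any cardiac abnormalities".

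For the C-SSRS, the table marks Visits 2, 3, 7, 8 and 11, while the visit text lists Visits 1, 2 and 11. At the end of block 1, section 6.4 reads: "Visit 6 will consist of ADHD-RS with prompts, Barkley SCT Scale, BRIEF-A, Barkley Functional Impairment Scale (BFIS), neuropsychological battery, CGI, vital signs", followed by adverse events and concomitant medication, with no C-SSRS. At the end of block 2, section 6.8 includes it: "Barkley Functional Impairment Scale (BFIS), C-SSRS, neuropsychological battery, CGI, vital signs".

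**The concern.** A reader of the safety section will expect the named variables to say something about LDX against placebo. Two of the five are measured only before dosing. A third, the C-SSRS, is collected on different visits depending on which part of section 6 a site follows, and under both parts it is absent at the end of the first treatment block.

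Section 1.6.1 names depression and dysphoria among the reported effects of amphetamines and treats a change in mood as a reason to discontinue. The C-SSRS is the plan's dedicated suicidality instrument. If it is not collected late in block 1, that information cannot be recovered afterwards. Likewise, an absence of ECG or laboratory findings in the report could be taken as reassurance about LDX when it would only reflect the schedule.

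**Working it through.** There is no stated figure to reproduce. The check sets the schedule beside the visit text and asks what each would yield.

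**ECG and laboratory tests.** Scheduled visits: {1}. First dose: the morning after Visit 2 (section 6.2). Scheduled on-treatment values: 0 on LDX, 0 on placebo.

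**C-SSRS.** Days are from sections 6.2 to 6.8.

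| Visit | Day | Table | Text | LDX-first patient | Placebo-first patient |
|---|---|---|---|---|---|
| 1 | screening | no | yes | before dosing | before dosing |
| 2 | 0 | yes | yes | before dosing | before dosing |
| 3 | 7 | yes | no | LDX | placebo |
| 4, 5 | 14, 21 | no | no | LDX | placebo |
| 6 | 28 | no | no | LDX, end of block 1 | placebo, end of block 1 |
| 7 | 42 | yes | no | end of washout | end of washout |
| 8 | 49 | yes | no | placebo | LDX |
| 9, 10 | 56, 63 | no | no | placebo | LDX |
| 11 | 70 | yes | yes | placebo, end of block 2 | LDX, end of block 2 |

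Table and text disagree at Visits 1, 3, 7 and 8. They agree that Visit 6 has no C-SSRS and that Visit 11 has one.

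**Time on block treatment at each on-treatment C-SSRS.** Block 1 counts from Day 0 and block 2 from Day 42.
- Visit 3: 7 − 0 = 7 days
- Visit 8: 49 − 42 = 7 days
- Visit 11: 70 − 42 = 28 days
- Visit 6, the missing counterpart of Visit 11: 28 − 0 = 28 days

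**What the table supports.** Visit 3 against Visit 8 compares like with like at one week. The last available value is at 7 days in block 1 and 28 days in block 2, so carrying the last value to the endpoint would set week 1 against week 4. The interval without a C-SSRS runs from Day 7 to Day 42, which is 35 days (31 to 39 with the ±2-day windows).

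**What the text supports.** Only Visit 11 is on treatment. LDX-first patients are then on placebo and placebo-first patients on LDX, so a between-group comparison in block 2 remains and there is no within-patient comparison. The interval between Visit 2 and Visit 11 is 70 days.

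**Which drug-by-order cells are observed.** Code drug = 1 for LDX and order = 1 for LDX first. With values in both blocks, all four combinations occur, and the matrix [1, drug, order, drug × order] has rank 4 of 4. With Visit 11 alone, drug = 1 − order and drug × order = 0 for everyone, so the rank is 2 of 4 and drug cannot be separated from order.

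**Patients affected.** The treatment phase takes 50 patients (sections 3.1 and 7.1). Section 5.3 gives no allocation ratio. If a share p starts on LDX, the number without an end-of-LDX C-SSRS is 50 × p: 25 at p = 0.5, and 20 to 30 for p between 0.4 and 0.6.

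**Cardiac wording.** After screening, the only scheduled cardiovascular measurement is vital signs, at Visits 2 to 11. Week 5 is a telephone contact.

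**The case against.** The strongest objection concerns what section 7.2 promises. A reader might infer that the C-SSRS, ECG and laboratory results are to be modelled by drug and order, and that the plan therefore specifies analyses that cannot be run. The text does not support this. Those variables are to be summarised and listed, which screening data allow. The models with drug, order and their interaction follow the sentence on adverse events and refer back to it. The rank calculation therefore shows what C-SSRS data could support, not that a prespecified C-SSRS model fails.

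It would also be too strong to say that no C-SSRS comparison is possible. Under the table, both blocks have on-treatment values and a week-1 comparison is sound. Under the text, Visit 11 still gives a randomised comparison between groups.

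The table itself may be unreliable here. The CANTAB, BRIEF-A and BFIS rows are marked at Visits 2, 7, 8 and 11, while sections 6.4, 6.6 and 6.8 place them at Visits 6, 7 and 11. Dispensing is marked at Visit 11, where section 6.8 mentions none. If the first four C-SSRS marks are also one column late, they become Visits 1, 2, 6 and 7, which would match the text at Visits 1 and 2 and give an end-of-block-1 value. Whether the displacement lies in the protocol or in the reading of the PDF cannot be settled. Section 6.4 omits the C-SSRS either way, so the discrepancy remains, and the displacement is an argument for the fix.

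Other safeguards exist. Adverse events are asked about at every contact (section 8.2), including the week 5 call. Section 4.2 excludes current suicidal ideation and past attempts. Section 8.1 allows for further or repeat tests, so the zero counts apply to scheduled tests only. These points reduce the risk to patients, but they do not replace the instrument that 7.2 says will be summarised. Unscheduled tests, done because something was suspected, would not give a comparison either.

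**Conclusion.** The concern stands as a mismatch between the listed safety variables and the schedule, and as an unresolved conflict within section 6. Scheduled ECG and laboratory data describe screening status only and support no LDX–placebo statement. The C-SSRS supports no end-of-treatment comparison across both blocks: the table allows a like-for-like comparison at week 1 only, and the text allows only a between-group comparison at Visit 11. About 25 of 50 patients, assuming equal allocation to the two orders, have no scheduled C-SSRS on LDX after Day 7 under the table, and none on LDX at all under the text.

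The ECG and laboratory conclusion does not depend on how the table is read. The C-SSRS conclusion takes section 6 as written; if the table's C-SSRS marks are displaced, Visit 6 was probably intended and section 6.4 is what needs correcting. The efficacy analyses are unaffected. This is a cheap improvement, not an error that invalidates a planned analysis.

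**What to change.** 1. Add the C-SSRS at Visit 6 in both section 6.4 and the schedule table, so that each block has an end-of-block value.
2. Reconcile the table with sections 6.1 to 6.8 for the C-SSRS at Visits 1, 3, 7 and 8, and check the other rows that look displaced at the same time.
3. In section 7.2, state that ECG and laboratory results are summarised at screening only and support no LDX–placebo statement. State which of the remaining safety variables are compared between treatments, and at which visits.
4. Reconcile the reference in section 1.6.1 to monitoring for any cardiac abnormality with the assessments that are scheduled.

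The cost is one short questionnaire at a visit that already takes place, plus protocol wording. The stated scope of the ECG and laboratory safety evaluation becomes narrower, but it will then match what the trial measures.

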### **5.2 Treatment Regimen**

Medication will not be dispensed until week 1 of the study. Then for four weeks the dose of LDX or Placebo will be dispensed starting at 30mg up to 70 mg per day with an intervening single-blind placebo washout period (2 weeks).

Block One: During the LDX/epoch, LDX/Placebo treatment will be initiated at a dose of 30mg/day at Visit 2 and can be titrated up (in the judgment of the investigator) in

CONFIDENTIAL

increments of 20mg, based upon clinical response and tolerability, to 50mg/day at Visit 3 and 70mg/day at Visit 4.

Subjects receiving daily doses of 50mg or 70mg of LDX/Placebo will be allowed to down titrate one dosage step of 20mg during Visits 3-5 if (in the judgment of the investigator) they are having issues in tolerability. The highest effective dose of LDX will then be maintained until Visit 6.

Placebo Washout: At this time the patient are in the washout placebo phase for two weeks.

Block Two: At the end of the Placebo Washout Phase, Visit 7 (week 6), participants will be initiated at a dose of 30mg/day and can be titrated up starting at Visit 8 (in the judgment of the investigator) in increments of 20mg, based upon clinical response and tolerability.

Subjects receiving daily doses of 50mg or 70mg of LDX/Placebo will be allowed to down titrate one dosage step of 20mg during Visits 8-10 if (in the judgment of the investigator) they are having issues in tolerability. The highest effective dose of LDX will then be maintained until Visit 11

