### **5.3 Method for Assigning Subjects to Treatment Groups**

Due to the study being double blind, an unblinded research assistant will conduct the block randomization of the subjects under the supervision of the NYU pharmacy. The block randomization will choose patients to start either the Vyvanse or placebo phase for four weeks. After these four weeks there will be a two week washout, then again Vyvanse or placebo phase for another four weeks. At the end of the study, the patients will be asked safety questionnaires. The patient and the research staff will not know whether the patient is on Vyvanse or placebo. In case of an emergency, the pharmacy can break the blind with permission from the principal investigator. We will know if the patient is on Vyvanse or placebo after the blind is broken.

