## 7.2 Statistical Methods

Phenotype Phase: Comparisons between the adult ADHD patients cohorts with SCT and without SCT in terms of ADHD symptoms (total, inattentive and hyperactive-impulsive, symptoms of executive function (BRIEF GEC, metacognition, behavioral regulation scales and subscales: Inhibit, Shift, Emotional Control, Initiate, Working Memory, Plan/Organize, Organization of Materials, Monitor), neuropsychological tests (CANTAB ADHD module, WAIS Coding and Symbol Search and Attention Network Test (ANT), and impairment (on Barkley Functional Impairment Scale (BFIS)) will be examine via One Way ANOVA .

Treatment Phase: Changes in outcome ratings in the patients in the treatment phase with LDX and placebo will be modeled with longitudinal generalized estimating equation (GEE) mixed regression models using STATA 12.0 [StataCorp, 2011 #25856] within the framework of the general linear model (GLM). The GLM allows us flexibility in modeling the outcome variable by choosing the appropriate distribution and link function. Each model will predict outcome scores from treatment group (drug vs. placebo), study visit (ordinal predictor), order (drug or placebo first) and the two and three-way interactions among: treatment group, visit, and order. We will first test for order effects and drop effects that are not significant at  $p < .05$ . The visit by treatment interaction indicates if the reduction in symptoms over time significantly differs between drug and placebo. Our primary analyses will be intention

CONFIDENTIAL

[SHIRE SCT s13-01288]  
Version: 03/03/2016

to treat (ITT) but we will explore the data with less conservative per protocol analyses to assure that we do not miss any signals in the data. Because this is a randomized trial, which follows subjects over a short period of time, missing data is not expected to impact our analyses. Should this become an issue, we will impute data using STATA's impute procedure. Using logistic regression, a responder analysis will be conducted using pre-hoc priori criteria for treatment response (30% decreases in total ADHD-RS and Barkley SCT scores). These will be last observation carried forward (LOCF) endpoint models that predict responder status (yes/no) from drug group, order and the drug by order interaction. Baseline symptom scores will be included as covariates.

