## **8.2 Recording of Adverse Events**

At each contact with the subject, the investigator must seek information on adverse events by specific questioning and, as appropriate, by examination. Information on all adverse events should be recorded immediately in the source document, and also in the appropriate adverse event module of the case report form (CRF). All clearly related signs, symptoms, and abnormal diagnostic procedures results should be recorded in the source document (though should be grouped under one diagnosis).

All adverse events occurring during the study period must be recorded. The clinical course of each event should be followed until resolution, stabilization, or until it has been determined that the study treatment or participation is not the cause. Serious adverse events that are still ongoing at the end of the study period must be followed up to determine the final outcome. Any serious adverse event that occurs after the study period and is considered to be possibly related to the study treatment or study participation should be recorded and reported immediately.

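### The adverse-event tests use an LOCF endpoint without defining the outcome; read naturally, events that resolve within a block drop out of the LDX–placebo comparison

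*Combined protocol and SAP*

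**What the plan says.** Section 7.2 (Safety Analysis) sets out both description and testing. On description: "Variables to be summarized and listed include vital signs, adverse events, clinical laboratory results, ECG readings, and the C-SSRS". On testing: "All adverse events results will be tabulated in manuscripts along with significance testing using the appropriate general linear model". The next sentence fixes the form of the tests: "These models will use LOCF endpoint analyses with terms for drug, order and the drug by order interaction". No other test of adverse events is planned, and the outcome that enters the model is not defined. It could be presence at the last visit, any occurrence in the block, a count or a severity grade.

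The same section uses the LOCF endpoint term once before, for response: "These will be last observation carried forward (LOCF) endpoint models that predict responder status (yes/no") from drug, order and their interaction. There it means one yes/no value per patient per treatment, taken from the last observation.

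Three other places bear on the point:

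- Section 8.2: "All adverse events occurring during the study period must be recorded". The schedule in Section 6 has adverse events assessed at every treatment visit and at the block ends (Visits 6 and 11).
- Section 5.2: patients on the two higher doses "will be allowed to down titrate one dosage step of 20mg during Visits 3-5" for tolerability, with the same allowance at Visits 8–10 in block two. Both windows close before the block-end visit.
- Section 1.6.1 has patients with certain listed central nervous system effects discontinued, and Section 8.5 lists adverse events as a reason for termination.

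**The concern.** LOCF endpoint analysis suits a score measured at each visit, where the last value summarises the state reached. An adverse event is an occurrence, and the usual safety question is whether it happened on treatment.

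If the outcome is status at the last observation, an event that appears in week 1 and has gone by Visit 6 contributes nothing to the test. This matters here because each block is a four-week titration. Tolerability events may be expected early, and Section 5.2 provides a dose step-down that may clear them before the endpoint. The tests would then set aside data that the trial already collects, and the resulting p-values are to be published beside the adverse-event tables. With about 40 to 50 patients, the tests have little power to spare.

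**Working it through.** **The plan's own figures.** There are none for adverse events: no expected rate, power or alpha. The only power statement (Section 3.1: 45 evaluable patients, effect size 0.6, 80%) concerns efficacy and has no bearing here.

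**Inputs.**

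- 44 pairs. Section 3.1 projects 44 patients completing the washout, so about 44 could contribute to both blocks.
- Assumed, because the documents give no figures: incidence per block I_L = 40% on LDX and I_P = 15% on placebo; latent (bivariate normal) within-patient correlation 0.3; resolution before block end independent between blocks, with shares r_L and r_P.
- Test: exact two-sided McNemar at 0.05.

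**Formulas.** Endpoint prevalence is E = I × (1 − r). The endpoint difference is therefore

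E_L − E_P = (I_L − I_P) − (I_L × r_L − I_P × r_P).

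It is smaller than the any-occurrence difference only when I_L × r_L > I_P × r_P. At 40% and 15%, that means unless r_P exceeds 40/15 = 2.67 times r_L.

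The probability of an event in both blocks is 0.088 for any occurrence, and 0.088 × (1 − r_L) × (1 − r_P) at the endpoint. The discordant probabilities follow by subtraction. For any occurrence they are 0.400 − 0.088 = 0.312 and 0.150 − 0.088 = 0.062. With half resolved in both blocks they are 0.200 − 0.022 = 0.178 and 0.075 − 0.022 = 0.053.

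**Results.**

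| Outcome scored | r_L / r_P | LDX vs placebo | Difference (points) | Power |
|---|---|---|---|---|
| Any occurrence | – | 40% vs 15% | 25 | 76% |
| Endpoint | 25% / 25% | 30% vs 11.25% | 18.8 | 53% |
| Endpoint | 50% / 50% | 20% vs 7.5% | 12.5 | 29% |
| Endpoint | 75% / 75% | 10% vs 3.75% | 6.3 | 8% |
| Endpoint | 50% / 25% | 20% vs 11.25% | 8.8 | 13% |
| Endpoint | 25% / 50% | 30% vs 7.5% | 22.5 | about 75% |
| Endpoint | 10% / 50% | 36% vs 7.5% | 28.5 | 91% |

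With equal resolution the risk ratio stays at 40/15 = 2.67. Only the absolute difference and the power fall.

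**Events that end treatment.** Suppose 20% of LDX events lead to withdrawal and are carried forward as present, and half of all other events resolve. Then E_L = 0.40 × (0.2 + 0.8 × 0.5) = 24% and E_P = 7.5%. The difference is 16.5 points and the power 48%, against 12.5 points and 29% without withdrawals.

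**Other assumptions.** With 40 pairs, 30% vs 10% and independent responses, power is 51% for any occurrence and 34%, 18% and 3% at equal resolution of 25%, 50% and 75%. At the same incidences, resolution of 75% on LDX and 25% on placebo leaves 7.5% in each block, a difference of zero.

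**The case against.** The strongest reply is that the plan never says a resolved event counts as absent. That is true: the outcome is undefined, and last-observation status is an inference. It is nevertheless the natural inference, because the responder models in the same section use the same term with the same model terms for a yes/no outcome. An undefined outcome also needs repair in its own right.

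A reader might infer that the plan hides harm on LDX. The documents do not support this. All events must be recorded, listed and tabulated, and Section 7.2 does not restrict the tables to the endpoint. Only the significance tests are affected, and the plan attaches no hypothesis, alpha or power to them.

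A reader might also infer that the LDX excess is bound to be understated. It is not. The direction depends on resolution in both blocks, and the documents give no rates. Carrying the last observation forward also keeps an event that is present at withdrawal. That softens the loss, but does nothing for patients who step down in dose and stay in the trial.

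Three further inferences go too far.

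- That the models ignore pairing because no patient term is listed: Section 7.2 places GEE within the general linear model framework, and GEE handles pairing by clustering rather than by a listed term. Whether this carries over to adverse events is unstated, so absence of clustering is not established.
- That a period term is missing: in a two-period, two-sequence cross-over, the drug-by-order interaction is the period contrast.
- That vital signs are caught by the same rule: the LOCF sentence refers to the adverse-event models, while vital signs are to be summarised and listed.

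**Conclusion.** The point stands in conditional form. Section 7.2 applies an LOCF endpoint to adverse-event tests and leaves the outcome undefined. Followed in the sense the section itself gives the term, the tests lose events that start and resolve within a block, including those that clear after a tolerability step-down.

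A smaller absolute difference and lower power are the likely result. At the assumed 40% and 15%, equal resolution of 25% to 75% takes the difference from 25 points to between 18.8 and 6.3, and the power from 76% to between 53% and 8%. Unequal resolution widens the range to 8.8 points with 13% power in one direction and 28.5 points with 91% in the other. These figures rest on assumed incidences, correlation and resolution shares, and illustrate the mechanism rather than forecast this trial. The primary efficacy analysis and the descriptive safety tables are untouched, so this is a change that should be made to secondary safety tests, not a threat to the main result.

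**What to change.** In Section 7.2 (Safety Analysis), replace the LOCF endpoint for adverse events with a defined outcome: any treatment-emergent occurrence or worsening within the block, scored yes or no per patient per block, in the all-treated population of Section 7.3.

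Keep the drug, order and drug-by-order terms, and state that the model is paired or clustered on patient, for example GEE with a logit link or conditional logistic regression. GEE can also use patients who contribute only one block. Conditional logistic regression cannot, and the order main effect drops out of it because order is constant within patient.

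Reserve the LOCF endpoint, if it is kept at all, for measured safety variables.

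The cost is SAP wording only. Events are already assessed at every treatment visit and recorded whether or not they resolve, so no visit, form or procedure changes. The wording should be settled before unblinding.
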